### 14.2 Statistical analysis

Continuous baseline characteristics for each of the PCOS OSA and PCOS low risk OSA groups will be summarised using the mean ( $\pm$ SD) and the median (interquartile range). If the data are approximately normally distributed, the means for the two groups will be compared using the independent t-test. If the data are not normally distributed, the two groups will be compared using the Mann-Whitney U test. Data will be checked for normality using the Shapiro-Wilk test (Razali and Wah 2011). Categorical baseline characteristics for each of the PCOS OSA and PCOS low risk OSA groups will be summarised by reporting the count and percentages in each category. The two groups will be compared using the chi-squared test.

To compare quality of life for the PCOS OSA and PCOS low risk OSA groups, we will fit linear models for each of the primary outcomes of interest (domain scores on the PCOSQ and WHOQOL-BREF questionnaires). The dependent variable in a linear model will be a primary outcome and independent (predictor) variable of interest will be whether a woman is from the PCOS OSA or PCOS low risk OSA group. As the groups may be imbalanced in other predictors for the primary outcomes, the models will adjust for potential confounders such as age, BMI, WHR, use of oral contraceptive pill, ethnicity, education level, marital status, other ongoing illnesses, and parity. Data will be assessed if they are approximately normally distributed; and if they are not, they will be transformed, for example, by taking the logarithm of the outcome variables.

Correlations will be evaluated using Pearson's coefficient (or Spearman's coefficient for non-normally distributed data). A two tailed P value of <0.05 will be considered statistically significant. Statistical analysis will performed using the SPSS statistics package (SPSS Inc., Chicago, USA).

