## 8. Study aims

Primary outcome:

- To examine if OSA is associated with impaired QoL in women with PCOS.

Secondary outcomes:

- To assess the relationship between OSA and body composition, hirsutism (modified Ferriman-Gallwey score), period cyclicality, reproductive outcomes, insulin resistance (HOMA-IR), hyperandrogenism, depression and anxiety, FPG, glycated haemoglobin (HbA1C), reproductive hormone profile, lipids, and inflammation (high sensitivity C-reactive protein, hCRP) in women with PCOS.

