### 13.6 Quality of life

QoL will be assessed using the PCOS health-related quality of life questionnaire (PCOSQ), and the World Health Organisation QoL questionnaire (WHOQOL-BREF). We will not be using an OSA disease-specific QoL questionnaire as only a proportion of study participants will have OSA and subsequently such a questionnaire will not reflect the QoL in controls well.

The PCOSQ (Cronin et al. 1998) is a validated method of assessing QoL in women with PCOS. It is the only PCOS condition-specific measure of QoL. The PCOSQ includes 26 items (questions) to cover 5 domains which were found to be of most importance to women with PCOS: emotions (8 items),

body hair (5 items), weight problems (5 items), menstrual problems (4 items) and infertility (4 items). Each item is scored out of 7, in which a score of 7 denotes no problems or difficulties and a score of 1 indicates maximum impairment. Each domain score is calculated by dividing the total score of all items within a domain by the number of items in that domain. The PCOSQ takes 10–15 minutes to complete and lower scores suggest impaired QoL. The PCOSQ has been found to demonstrate acceptable internal consistency (0.70–0.97) and test-retest reliability (Malik-Aslam et al. 2010). A difference of 0.5 on the 1 to 7 scale has been suggested to represent the minimal important difference in the questionnaire score, i.e. the smallest change in score that women feel is important in their daily lives (Cronin et al. 1998).

The WHOQOL-BREF (Skevington and McCrate 2012) is a validated generic measure of QoL. It includes 26 questions to assess four major domains (subscales): physical, psychological, social and environment. Scores are given out of a hundred and higher scores are better; a score of more than 50% indicates an acceptable to good QoL. The WHOQOL-BREF has been shown to display high internal consistency (0.92); good test-retest reliability (0.66 – 0.72); discriminant validity (discriminating sick from healthy people), and content validity (correlation with the Short Form 36 Health Survey (SF-36)) (Skevington and McCrate 2012). WHOQOL-BREF provides a very good holistic assessment of QoL in the general population and its validation study included a group of women with PCOS, and a group of people with sleep disorders (Skevington and McCrate 2012).

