## 14. Statistical considerations

### 14.1 Sample size calculation

The QoL between the two groups will be compared based on the PCOSQ and the WHOQOL-BREF questionnaires.

The validation study for the WHOQOL-BREF (Skevington and McCrate 2012) included a group of people with sleep disorders and a group of healthy controls. Based on this study a total sample size of 38 participants will give us 80% power, and 5% significance (two-tailed), to detect a mean difference of 17.8 on one item of the WHOQOL-BREF (large effect size 0.98) between cases (PCOS OSA) and controls (PCOS low risk of OSA), **Table 3**. We used an allocation ratio for cases/controls of 0.67, 40% of participants in the PCOS OSA group, and 60% in the PCOS low risk OSA group. Sample size was calculated using GPower 3.1.

	Well n=141		Sleep disorders group n=45		Pooled SD	Mean difference	Effect size	n/ PCOS OSA group	n/PCOS low risk OSA group	Total sample
Item	Mean	SD	Mean		SD					
Physical Health	75.41	18.72	57.65	17.67	18.2	17.8	0.98	15	23	38

**Table 3.** Difference in WHOQoL-Bref scores on the physical health item between people with sleep disorders breathing and healthy controls (Skevington and McCrate 2012).

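### Nine questionnaire domain scores are all primary at P<0.05 with no lead domain or success rule, while the stated 5% and 80% apply to only one of them

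*Combined protocol and SAP*

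**What the plan says.** All of this is in the combined protocol and SAP.

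- **Primary question (section 8).** There is one: "To examine if OSA is associated with impaired QoL in women with PCOS". No instrument or domain is named.
- **Primary analysis (section 14.2).** The outcomes are plural: "we will fit linear models for each of the primary outcomes of interest (domain scores on the PCOSQ and WHOQOL-BREF questionnaires"). All domains are treated alike.
- **Number of domains (section 13.6).** "The PCOSQ includes 26 items (questions) to cover 5 domains"; for the WHOQOL-BREF, "It includes 26 questions to assess four major domains (subscales): physical, psychological, social and environment".
- **Threshold (section 14.2).** "A two tailed P value of <0.05 will be considered statistically significant". This is the only significance threshold given for the analysis.
- **Sample size (section 14.1).** The section opens with both instruments: "The QoL between the two groups will be compared based on the PCOSQ and the WHOQOL-BREF questionnaires". The calculation then covers a single score, with 38 women giving 80% power at two-sided 5% "to detect a mean difference of 17.8 on one item of the WHOQOL-BREF". Table 3 shows that this score, labelled an item, is the WHOQOL-BREF physical health domain.

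The documents contain no testing order, no multiplicity adjustment, and no statement of how many domains, or which, must be significant.

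**The concern.** The study asks one primary question and plans nine primary tests, with nothing to connect the two. Once the data are in, one significant domain out of nine could be reported as showing that OSA is associated with impaired quality of life. So could a pattern across several domains, or a result on one instrument only. The choice would be open after the results are known.

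The 5% and 80% in section 14.1 hold for physical health tested alone. They do not hold for the set of nine that section 14.2 calls primary. A reader who takes them as properties of the primary analysis would overrate the strength of a positive finding. None of the five PCOSQ domains and none of the other three WHOQOL-BREF domains has a power statement.

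**Working it through.** **Inputs**

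- Number of primary outcomes: 5 + 4 = 9 (section 13.6).
- Threshold: two-sided 0.05 per test (section 14.2).
- Sizing: difference 17.8, pooled SD 18.2, effect size 0.98, groups of 15 and 23 (section 14.1, Table 3).
- Correlation between domains: not given. I assume one common value r and show a range.

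**1. The plan's own figure**

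Effect size: 17.8/18.2 = 0.978, stated as 0.98. For a two-sample t-test with 15 and 23 women, df = 15 + 23 − 2 = 36. The noncentrality is 0.98 × √(15 × 23/38) = 0.98 × 3.013 = 2.95. Noncentral-t power at two-sided 0.05 is 81.9%. The total of 38 is confirmed for this one domain.

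**2. Chance of at least one false positive among nine tests**

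This assumes no true OSA effect and that any one significant domain is read as an association.

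For independent tests, either direction: 1 − 0.95^9 = 0.370. In the impaired direction only (0.025 per test): 1 − 0.975^9 = 0.204.

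For a common correlation r, with c = 1.96, φ the standard normal density and Φ its distribution function:

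- either direction: 1 − ∫ φ(u) [Φ((c − √r·u)/√(1−r)) − Φ((−c − √r·u)/√(1−r))]^9 du
- impaired direction only: 1 − ∫ φ(u) [Φ((c − √r·u)/√(1−r))]^9 du

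| r | Either direction (one test: 5%) | Impaired direction only (one test: 2.5%) |
|---|---|---|
| 0 | 37.0% | 20.4% |
| 0.3 | 32.6% | 16.5% |
| 0.5 | 26.9% | 13.5% |
| 0.7 | 20.2% | 10.1% |
| 0.9 | 12.4% | 6.2% |

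Simulated t-tests with 15 versus 23 women (100,000 trials per correlation) agree for the either-direction column: 36.9%, 32.6%, 27.4%, 20.5% and 12.7%.

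**3. Cost of adjusting over all nine**

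The Bonferroni level is 0.05/9 = 0.00556. With 15 versus 23 women and effect size 0.98, power for a given domain falls from 81.9% to 50.9%. The smallest total on a 40/60 split that reaches 80% is 61 (24 and 37), with power 80.06%. Fixing the ratio at 0.67 and rounding each group up gives 63 (25 and 38).

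**4. The opposite rule: all nine must be significant**

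If the effect size were 0.98 in every domain, simulated power with 15 versus 23 women would be about 17% at r = 0, 43% at r = 0.5 and 54% at r = 0.7. The stated 80% does not hold under this rule either.

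**The case against.** The strongest reply is that the plan never says one significant domain is enough, so the error rates above belong to one reading of it. That is true. Under a rule requiring at least five of nine domains, the simulated false-positive rate is about 0%, 1% and 2% at r = 0, 0.5 and 0.7. But the plan does not state that rule either. With no rule stated, the any-one-domain reading is open, and the 5% cannot be claimed for the primary analysis.

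Nine scores from the same women are also unlikely to be uncorrelated, so 37% is the top of a range and not an estimate. This stands, although the rate is still more than twice nominal at r = 0.9.

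Section 14.1 is open about covering one score, and sizing on physical health hints at a lead domain. However, no section designates it as one, and section 14.2 gives it no special place.

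The study is observational, assigns no treatment and has 38 women, so some would settle for full reporting with intervals. Against that, it states a directional hypothesis (section 7), a primary outcome and a design error rate, and nothing labels it exploratory.

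Finally, 51% is a floor for Holm, which is never less powerful than Bonferroni. If all nine domains truly had effect size 0.98, simulated Holm power for the sized domain would be about 62–63% at r = 0 to 0.7. That is still well short of 80%.

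**Conclusion.** The concern holds and must be fixed. As written, the primary analysis is nine co-equal tests at 0.05 with no rule linking them to the one primary question, and the stated 5% and 80% belong to one of the nine. If any single significant domain counts, the two-sided false-positive risk is 12% to 37% for common correlations from 0.9 down to 0. In the impaired direction alone it is 6% to 20%, against 2.5%.

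These figures rest on the any-one-domain reading, no true effect, and an assumed common correlation. The fall in power from 82% to 51% applies to an unadjusted t-test with Bonferroni. Section 14.2 plans covariate-adjusted models, whose power may differ and cannot be computed from the documents. That the plan lacks a lead domain and a success rule depends on none of these assumptions.

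**What to change.** **Preferred.** In sections 8 and 14.2, name the WHOQOL-BREF physical health domain as the single primary outcome, tested at two-sided 0.05. Make the other three WHOQOL-BREF domains and the five PCOSQ domains secondary. Report them with 95% confidence intervals, and either Holm-adjust across the eight or declare them exploratory. This changes wording only: the calculation in section 14.1 and the total of 38 stay, with no extra data. The real cost is that the PCOSQ, which section 13.6 presents as the only condition-specific measure, loses primary status. The sponsor should make that choice knowingly.

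**If the PCOSQ is to stay primary.** Apply Holm across all the primary domains, state in advance which results would support the hypothesis, and restate the power in section 14.1. With all nine kept, the cost is lower power for the sized domain (51% at the Bonferroni first step, unadjusted t-test) or a larger sample, about 61 women for 80% at that step.

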## **15. Ethical Considerations**

The study will be performed subject to favourable opinion from NHS Research Ethics Committee (REC), and the NHS Health Related Authority (HRA), and approvals from University Hospitals Coventry and Warwickshire NHS Trust Research and Development Department. Patients will be offered the PIS by a nurse while they are sitting in the waiting area before being seen in the PCOS clinic. The PIS and a study invitation letter will also be sent to patients who attended the PCOS clinic in the last 12 months.

We excluded women who do not speak adequate English from the study. However, almost all the women attending the PCOS clinic at University Hospital Coventry speak and understand English adequately.

We are asking study participants to fast before obtaining their written consent. However, these women will already have a confirmed diagnosis of PCOS as they will be recruited from the PCOS clinic. They will also have had enough time to read the PIS to consider whether they would like to take part in the study. When a patient calls back to express interest in the study and book a study visit, the study doctor will run through the inclusion/exclusion criteria with the patient and obtain her verbal consent on the phone to ensure she is happy to fast before attending the study visit and signing the written consent form. This will save the study participant time and effort, particularly as we are not paying for participants' transport or car parking fees.

Depending on the scores from the HAD scale, this study may result in the identification of women with PCOS who may suffer from depression or anxiety. Women with high scores on the HAD questionnaire will be advised to attend their GP for further evaluation of their mood.

Study participants who are sleepy during the daytime will be advised not to drive if feeling sleepy. Those with a confirmed diagnosis of OSA will be seen in the respiratory clinic and issues related to driving and DVLA regulations will be discussed with them by the Respiratory physician as per routine clinical care; this information will also be included in the PIS.

Women with high risk of OSA will be offered a portable sleep study machine to take home. Studies with less than 4 hours of good quality recordings will be repeated and if the quality remained poor they will be excluded from the study. However, this should not affect women's clinical care as all women with high risk of OSA will be referred to the Chest clinic.

## **16. Side effects**

There are no serious side effects to any of the study procedures. Taking blood samples may well cause discomfort and risks of inflammation/ infection/ bruising at the needle site. The procedure will be explained to the study participant before it is done to minimise the anxiety. The blood taking will be performed by an experienced study nurse or doctor in accordance with the local guidelines.

## **17. Insurance**

UHCW has agreed to act as sponsor for this trial and will undertake the responsibilities of sponsor as defined by the Research Governance Framework and ICH Good Clinical Practice. An authorised representative of the Sponsor has approved the final version of this protocol with respect to the trial design, conduct, data analysis and interpretation and plans for publication and dissemination of results. As sponsor, UHCW provides indemnity for this trial and, as such, will be responsible for

claims for any non-negligent harm suffered by anyone as a result of participating in this trial. The indemnity is renewed on an annual basis and will continue for the duration of this trial.

### **18. Funding**

[name] is an NIHR clinical lecturer in Diabetes and Endocrinology and 50% of his time is allocated to research and funded by NIHR.

### **19. Public and Patient Involvement**

We discussed the study with seven patients attending the PCOS clinic at University Hospital Coventry. All women felt the study is important particularly as it may help women with PCOS to understand their condition better and may help explain some of their symptoms. They also felt the study may help to identify women with PCOS who suffer with OSA and may benefit from treatment. Five out of the seven women said they will be happy to take part in a similar study and one woman said she will consider it.

### **20. Reporting and dissemination**

Results from the study will be presented in the British and/or International Endocrine Society Meetings, and we aim to publish the results of the study in high impact peer-reviewed Endocrinology journals. Study participants will be asked if they want to be informed about study results and if they do a summary of the research findings will be sent to them.

### **21. Annual Progress Reports**

An annual progress report will be submitted to the main REC which gave the favourable opinion 12 months after the date on which the favourable opinion was given and thereafter until the end of the study.

### **22. Data handling and record keeping**

All information that is collected about you during the course of the research will be kept strictly confidential. Paper study documents will be retained in a secure (kept locked when not in use) office located at the WISDEM centre, University Hospital Coventry, during and after the study has finished. Electronic data will be stored on University Hospitals Coventry and Warwickshire NHS Trust computers, which are password protected and user-access restricted to authorised persons in adherence to Trust information Governance Policy. The authorised persons who may have access to the study data include study researchers, regulatory authorities, and people monitoring the quality of the research at University Hospital Coventry. If data is transferred electronically, for example to analyse on a University computer, the data will be encrypted and linked anonymised, i.e. it will have participant's name, date of birth, and address removed and replaced with participant's study ID number. Only the study researchers will be able to link the study ID and participant's personal details. Data will be collected and retained in accordance with the Data Protection Act 1998. Data (paper and electronic) will be held for a total of 25 years.

### **23. Monitoring and Auditing**

The study will be monitored by the Research, Development and Innovation Department at UHCW as representatives of the Sponsor, to ensure that the study is being conducted as per protocol, adhering to Research Governance and GCP. The approach to, and extent of, monitoring will be

specified in a study monitoring plan determined by the risk assessment undertaken prior to the start of the study.

#### **24. End of study**

End of the study is the date of the visit of the last study participant. An end of study declaration form will be sent to the main REC and sponsor within 90 days of the end of the study or within 15 days if the study is terminated early.

## **Appendix:**

1. Modified Ferriman-Gallwey Score.
2. Epworth Sleepiness Scale (ESS).
3. Berlin Questionnaire.

## 1. Modified Ferriman-Gallwey Score

Each of the nine body areas is rated from 0 (absence of terminal hairs) to 4 (extensive terminal hair growth) and the numbers in each area are added to obtain the total score. A total score  $\geq 8$  generally defines hirsutism (Ferriman and Gallwey 1961; DeUgarte et al. 2006).

## 2. Epworth Sleepiness Scale (ESS)

**Epworth Sleepiness Scale**

Name: \_\_\_\_\_ Today's date: \_\_\_\_\_

Your age (Yrs): \_\_\_\_\_ Your sex (Male = M, Female = F): \_\_\_\_\_

How likely are you to doze off or fall asleep in the following situations, in contrast to feeling just tired?

This refers to your usual way of life in recent times.

Even if you haven't done some of these things recently try to work out how they would have affected you.

Use the following scale to choose the **most appropriate number** for each situation:

0 = would never doze  
1 = slight chance of dozing  
2 = moderate chance of dozing  
3 = high chance of dozing

*It is important that you answer each question as best you can.*

Situation	Chance of dozing (0-3)
Sitting and reading _____	
Watching TV _____	
Sitting, inactive in a public place (e.g. a theatre or a meeting) _____	
As a passenger in a car for an hour without a break _____	
Lying down to rest in the afternoon when circumstances permit _____	
Sitting and talking to someone _____	
Sitting quietly after a lunch without alcohol _____	
In a car, while stopped for a few minutes in the traffic _____	

A score more than 10 on the ESS suggests an increased risk of OSA (Johns 1991; Greenstone and Hack 2014).

### 3. Berlin Questionnaire

#### Berlin Questionnaire® Sleep Apnea

Height (m) \_\_\_\_\_ Weight (kg) \_\_\_\_\_ Age \_\_\_\_\_ Male / Female

Please choose the correct response to each question.

##### Category 1

1. Do you snore?

- a. Yes
- b. No
- c. Don't know

*If you answered 'yes':*

2. Your snoring is:

- a. Slightly louder than breathing
- b. As loud as talking
- c. Louder than talking
- d. Very loud. Could be heard in adjacent rooms.

3. How often do you snore?

- a. Almost every day
- b. 3-4 times per week
- c. 1-2 times per week
- d. 1-2 times per month
- e. Rarely or never

4. Has your snoring ever bothered other people?

- a. Yes
- b. No
- c. Don't know

5. Has anyone noticed that you stop breathing during your sleep?

- a. Almost every day
- b. 3-4 times per week
- c. 1-2 times per week
- d. 1-2 times per month
- e. Rarely or never

##### Category 2

6. How often do you feel tired or fatigued after your sleep?

- a. Almost every day
- b. 3-4 times per week
- c. 1-2 times per week
- d. 1-2 times per month
- e. Rarely or never

7. During your waking time, do you feel tired, fatigued or not up to par?

- a. Almost every day
- b. 3-4 times per week
- c. 1-2 times per week
- d. 1-2 times per month
- e. Rarely or never

8. Have you ever nodded off or fallen asleep while driving a vehicle?

- a. Yes
- b. No

*If you answered 'yes':*

9. How often does this occur?

- a. Almost every day
- b. 3-4 times per week
- c. 1-2 times per week
- d. 1-2 times per month
- e. Rarely or never

##### Category 3

10. Do you have high blood pressure?

- Yes
- No
- Don't know

The test is suggestive of OSA if two or more categories were positive. Category 1 is positive if 2 or more responses were positive (shaded areas). Category 2 is positive if 2 or more responses were positive. Category 3 is positive if the patient had a history of hypertension or BMI>30kg/m^2 (Netzer et al. 1999).
